#### 3.2.3 Retrospective unsequenced prenatal group

Any changes to the prospective unsequenced prenatal group criteria are italicized below.

#### 3.2.3.1 Inclusion Criteria

- 1. Fetus identified by ultrasound and/or MRI with at least one of the following:
  - a. One or more suspected major structural anomalies (Appendix A)
  - b. A nuchal translucency measurement of  $\geq$  3.5 mm and < 4.5 mm without evidence of cystic hygroma
  - c. A fetus less than 24 weeks 0 days gestation with normal anatomy and sonographically estimated fetal weight <5th %ile without maternal hypertension, type I diabetes, or other maternal disorders known to alter fetal growth
- 2. Did not pursue prenatal sequencing
- 3. Singleton gestation or dichorionic diamniotic (DCDA) twin gestation.
- 4. Gestational age less than 36 weeks, 0 days at date study-specified anomalies first diagnosed

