### **Appendix A. Eligible Major Structural Anomalies**

Abdominal wall	Heart
Bladder exstrophy/Epispadia	Anomalous pulmonary venous return
Body-stalk anomaly	Aortic stenosis/atresia
Cloacal exstrophy	Arrythmia
Gastroschisis	ASD
Omphalocele	AV canal defect
CNS	Coarctation
Absent or hypoplastic cerebellar vermis	Dextrocardia
Agenesis of corpus collosum	Double outlet right vertricle (DORV)
Anencephaly/Acrania	Ebsteins anomaly
Arachnoid cyst	Heart tumor
Cerebellar hypoplasia	Hypoplastic left heart
Chiari malformation	Hypoplastic right heart
Dandy-Walker malformation	Interrupted aortic arch
Encephalocele	Myxoma
Heterotopia	Pulmonary stenosis/atresia
Holoprosencephaly	Tetralogy of Fallot
Hydranencephaly	Transposition
Iniencephaly	Truncus Arteriosus
Macrocephaly (relative to fetal size)	VSD
Megalencephaly	Single ventricle
Microcephaly	Tricuspid atresia/stenosis
Lissencephaly	VSD
Parenchymal defect (gyral anomaly)	NS cardiac (abn 4-chamber view/outflow tracts, atrial/vent dilation)
Posterior fossa cyst	Abdomen, intestine, and liver anomalies
Spina bifida	Abnormal adrenal glands (tumor, uncertain)
Tumor	Bladder (dilated tense/floppy, ureterocele, duplex system)
Vascular anomaly	Bilateral congenital hydronephrosis
Ventriculomegaly/Hydrocephaly	Echogenic kidney
Ear	Horseshoe kidney
Anotia	Large kidney
Outer ear malformation	Multicystic kidney
Neck	Pelvic kidney
Cystic hygroma	Polycystic kidney
Teratoma	Small kidney
A nonhtholmio/Migrantholmog	Multi-cystic renal dysplasia
Anophthalmia/Micropthalmos	Renal agenesis
Congenital cataract	Urethra (absent, dilated/valves)
Cyclopia	Skeletal Skeletal dynalogie
Hypertelorism	Skeletal dysplasia
Hypotelorism	Cloverleaf skull
Face	Hip dislocation/dysplasia
Facial tumor	Limb defect
Lip – Cleft	Foot (absent, oligo-/poly-/syn-dactyly, rocker bottom foot, split foot)
Genitalia	Hand (absent, brachy-/oligo-/ syn-dactyly, overlapping fingers,
Ambiguous genitalia	polydactyly (only if non-familial), split hand)
Hypospadias	Joints (fixed extended, fixed flexed)
Micropenis	Talipes
	Long bones (absent, bowed, short (<1st %ile), fracture)

14 Jan 2019
Skin
Congenital skin disorder
Hemangioma
Tumor, unspecified
Spine
Kyphosis
Sacral agenesis
Sacrococcygeal teratoma
Scoliosis
Sirenomelia
Thorax/Respiratory
Congenital diaphragmatic hernia
Choanal atresia
Congenital lung lesion/CCAM
Hydrothorax
Hypoplastic thorax
Bell-shaped thorax
Short ribs
Other (reviewed centrally prior to enrollment)

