	3.2.1, 3.2.2	Added the inclusion of dichorionic diamniotic twin gestations in which only one fetus has an eligible anomaly. Monochorionic diamniotic (MCDA) and monochorionic monoamniotic (MCMA) twins and a gestation in which both fetuses have an anomaly are excluded.	Improve generalizability of the results by including twin gestation. MCDA and MCMA are excluded due to the increased risk of adverse pregnancy outcomes.
	3.2.1.2, 3.2.2.2	Updated exclusion criteria to eliminate the need for delivery at a study center or associated hospital	This will allow enrollment of individuals who deliver at outside hospitals
	4.2.1	Clarified that either the twin with the anomaly or both twins will be sampled according to local clinical practice	The study only requires the twin with the anomaly to be sampled, but some sites sample both as part of clinical practice
	4.3	Clarified that data collection will include twin gestation	This will be collected in order to account for twin gestations
	4.5	Clarified that the reporting of secondary fetal findings will be per local site guidelines	This will allow sites to report secondary fetal findings during pregnancy
	4,6, 4.8	Clarified that for twin gestations, neonatal and cost data will only be collected for the twin with the anomaly	Outcomes will only be analyzed for the fetus with the anomaly

Date	Affected Section(s)	Summary of Revisions Made	Rationale
18 May 2021	3.2.1.2	Clarified exclusion criteria for the sequenced group so that only those with positive gene panels are excluded	This will allow those patients with negative gene panels to be included which could benefit from whole genome sequencing
	3.2.2.2	Clarified that CMA findings that are pathogenic or likely pathogenic as well as causal are excluded	Pathogenic or likely pathogenic variants that are related to the prenatal ultrasound finding will be excluded
	4.1	Updated eligibility flow chart to reflect changes to sample collection	Maternal buccal swab/saliva or blood may be collected
	4.2.1	Added that maternal buccal swab/saliva may be collected instead of blood	There are times when collecting blood is not feasible, and DNA can be extracted from either blood or saliva
	4.7.1	Clarified that there will be one interview between 2 weeks after results disclosure or 4 weeks after enrollment for the unsequenced group and 15 months after delivery	Each parent will be interviewed once, and the interview will be scheduled at some point during study follow-up

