# 4 Study Procedures

# 4.1 Screening for Eligibility and Consent

Eligible patients with specified fetal structural anomalies will be identified by prenatal ultrasound and/or fetal MRI. Center investigators and their staff in the outpatient ultrasound prenatal diagnostic units will be responsible for identifying eligible patients. To maximize recruitment, coordinators at each center will screen the prenatal diagnostic logs on a daily basis to identify eligible patients.

Upon recognition of a specified fetal anomaly, the maternal fetal medicine physician (MFM)/ ultrasonographer and/or a genetic counselor will explain the ultrasound finding as per routine clinical care. At the conclusion of the initial evaluation/consult, women will be informed by the physician/counselor and/or coordinator about the study. Once the potential participant indicates willingness to hear more about the study, a study coordinator will meet with the parents, review eligibility, and explain the study. Women who choose to undergo prenatal invasive testing will be approached for the prenatal sequencing group but will not be enrolled until a negative or non-causal karyotype/CMA is confirmed (with the exception of those enrolled into expedited prenatal sequencing, section 4.2.1). Women who choose not to have any diagnostic testing or decline sequencing will be approached for participation in the unsequenced prenatal group. A portion of the unsequenced group will be enrolled through medical record review under a waiver of consent. All women with a specified fetal anomaly will be recorded on a screening log that collects screening ID, date screened, planned invasive prenatal testing, ultrasound anomaly, screening status code and reason for study ineligibility (if applicable). A participant flowchart is shown in Figure 1.

Figure 1. Prospective screening flowchart

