#### 4.2.3 Retrospective unsequenced prenatal group

The retrospective unsequenced prenatal group will include participants from the screening log who did not actively decline enrollment and are otherwise eligible. Participants will be considered enrolled at the time of diagnosis of the fetal anomaly.

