# Appendix A. Eligible Major Structural Anomalies

Abdominal wall	Heart
Bladder exstrophy	Anomalous pulmonary venous return
Body-stalk anomaly	Aortic stenosis/atresia
Cloacal exstrophy	Arrhythmia
Gastroschisis	ASD
Omphalocele	AV canal defect
CNS	Coarctation
Absent or hypoplastic cerebellar vermis	Dextrocardia
Agenesis of corpus collosum	Double outlet right ventricle (DORV)
Anencephaly/Acrania	Ebsteins anomaly
Arachnoid cyst	Heart tumor
Cerebellar hypoplasia	Hypoplastic left heart
Chiari malformation	Hypoplastic right heart
Dandy-Walker malformation	Interrupted aortic arch
Encephalocele	Myxoma
Heterotopia	Pulmonary stenosis/atresia
Holoprosencephaly	Tetralogy of Fallot
Hydranencephaly	Transposition
Iniencephaly	Truncus Arteriosus
Macrocephaly (relative to fetal size)	VSD
Megalencephaly	Single ventricle
Microcephaly	Tricuspid atresia/stenosis
Lissencephaly	NS cardiac (abn 4-chamber view/outflow tracts, atrial/vent dilation)
Parenchymal defect (gyral anomaly)	115 Cardiae (abit 4-chamber view/outflow tracts, atrial vent diractor)
Posterior fossa cyst	Abdomen, intestine, and liver anomalies
Spina bifida	Abnormal adrenal glands (tumor, uncertain)
Tumor	Bladder (dilated tense/floppy, ureterocele, duplex system)
Vascular anomaly	Moderate/severe bilateral hydronephrosis/urinary tract dilation
Ventriculomegaly/Hydrocephaly	Echogenic kidney
Ear	Horseshoe kidney
Anotia	Large kidney
Outer ear malformation	Multicystic kidney
Neck	Pelvic kidney
Cystic hygroma	Polycystic kidney
Teratoma Teratoma	Small kidney
Eye	Multi-cystic renal dysplasia
Anophthalmia/Micropthalmos	Renal agenesis
Congenital cataract	Urethra (absent, dilated/valves)
Cyclopia Cataract	Skeletal
Hypertelorism	Skeletal dysplasia
Hypotelorism	Cloverleaf skull
Face	Hip dislocation/dysplasia
Facial tumor	Limb defect
Lip – Cleft	Foot (absent, oligo-/poly-/syn-dactyly, rocker bottom foot, split foot)
Genitalia	Hand (absent, brachy-/oligo-/ syn-dactyly, overlapping fingers,
Ambiguous genitalia	polydactyly (only if non-familial), split hand)
Epispadias	Joints (fixed extended, fixed flexed)
Hypospadias	Talipes
Micropenis	Long bones (absent, bowed, short (<1 st %ile), fracture)

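### Retrospective controls have no calendar window, so twin pregnancies from before 22 Dec 2021 can enter the charge comparison on the control side only

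*Combined protocol and SAP*

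**What the plan says.** Section 4.2.3 of version 1.8 says the retrospective unsequenced group "will include participants from the screening log who did not actively decline enrollment and are otherwise eligible". It gives no calendar window and does not say which protocol version decides eligibility. Section 4.1 states that "All women with a specified fetal anomaly will be recorded on a screening log"; the log also holds the reason for ineligibility, so it includes women who were screened out.

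Section 3.2.3.1 sets the plurality rule for these controls: "Singleton gestation or dichorionic diamniotic (DCDA) twin gestation". The sequenced group has the same rule in version 1.8 (section 3.2.1.1), but version 1.0 of 14 Jan 2019 allowed singletons only. Twins reduced early to a singleton were added on 18 Nov 2019. The amendment history for 22 Dec 2021 reads "Added the inclusion of dichorionic diamniotic twin gestations in which only one fetus has an eligible anomaly".

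Section 5.3 compares the sequenced group with prospective and retrospective controls combined for utilization, cost and perinatal outcomes. It first compares demographics and severity of ultrasound findings, and adjusts for covariates if differences appear. Section 4.3 collects twin gestation at baseline, and the amendment history gives the reason as being able to account for twins in the data. Section 5.3 does not mention plurality, protocol version or enrollment period.

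**The concern.** The charge comparison is not randomized, so it depends on the two groups having been selected by the same rules. A woman with a dichorionic twin pregnancy who was screened out before 22 Dec 2021 did not decline enrollment, and she meets the version 1.8 criteria. On a plain reading she is available as a control, while her counterpart could not have been in the sequenced group.

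If twin pregnancies carry higher hospital charges than singletons, their presence on one side only raises the control charges and imitates a saving from sequencing. That twins cost more is an assumption here; the documents do not say so. Retrospective controls may be numerous, because the amendment history explains that prospective enrollment of the unsequenced group was not feasible.

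**Working it through.** **Timeline.** From version 1.0 (14 Jan 2019) to twin eligibility (22 Dec 2021) is 35.3 months. Section 9.2 plans 270 sequenced patients a year, so 750 / (270/12) = 33.3 months. On that plan, sequenced accrual starting at version 1.0 would have ended before twins became eligible. Actual accrual dates are not in the documents.

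**The plan's own power figure.** Inputs from section 5.1: mean charge 277,902, SD 389,484, lognormal; 500 sequenced and 300 controls; mean ratio 0.80; two-sided alpha 0.05.

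- Log-scale SD = sqrt(ln(1 + (389,484/277,902)²)) = 1.042.
- SE of the log ratio = 1.042 × sqrt(1/500 + 1/300) = 0.0761.
- Power at ln(0.80) = -0.223 is 83.4% for the log-scale z-test and 81.7% for the Mann-Whitney test (efficiency 3/π).

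The stated 80% is consistent with the Mann-Whitney figure and is not in dispute.

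**Size of the twin effect.** Let t be the excess share of twins among controls and k their charge ratio to singletons. Both are assumed.

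- Control mean multiplier: 1 + t(k - 1).
- Shift in mean log charge: t × ln(k), because only the twin subset is shifted.
- Type I error with no true effect: Φ(-1.96 + t ln k / 0.0761) + Φ(-1.96 - t ln k / 0.0761).

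| t | k | Control mean multiplier | Log shift | Type I error |
|---|---|---|---|---|
| 1% | 1.5 | 1.005 | 0.0041 | 5.0% |
| 3% | 1.5 | 1.015 | 0.0122 | 5.3% |
| 3% | 2 | 1.03 | 0.0208 | 5.9% |
| 6% | 2 | 1.06 | 0.0416 | 8.5% |
| 10% | 2.5 | 1.15 | 0.0916 | 22.5% |

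Section 5.3.1 reports costs as means, so the multiplier matters as well as the test.

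**Would the adjustment rule catch it?** Suppose plurality were among the variables compared. With no twins among 500 sequenced, 3 twins among 300 controls give Fisher p = 0.052 and 4 give p = 0.020. Nine twins (3%) give p = 0.0001. A significance trigger would miss up to 3 twins (1%), where the bias is negligible, and would flag the larger imbalances. The weakness is that section 5.3 does not put plurality among the variables compared.

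**The case against.** The strongest reply is that the text can be read otherwise. Section 4.2.3 treats a retrospective control as enrolled when the anomaly is diagnosed, and its eligibility condition could mean eligible under the criteria of that date. On that reading no early twin enters. This is possible, but section 3.2.3 gives the group its own criteria with no date or version qualifier. The two readings yield different control groups, so the choice should be written down.

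A second reply is that the plan already has safeguards. Twin status is collected, adjustment follows when differences are found, and sections 4.6 and 4.8 limit neonatal and charge information to the affected twin, which limits the charge ratio. All of this stands, and it makes the larger scenarios less likely to go unnoticed. It does not give plurality a place in the analysis.

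A reader might also infer that hydronephrosis and nuchal translucency split the groups in the same way. Appendix A changed from "Bilateral congenital hydronephrosis" in version 1.0 to "Moderate/severe bilateral hydronephrosis/urinary tract dilation" in version 1.8 (logged 15 Jun 2020), and an upper limit of 4.5 mm was put on the nuchal translucency criterion on 13 Nov 2020. A period-limited mismatch is possible. However, both changes are logged as clarifications, version 1.0 already required a major anomaly, and nothing shows that mild hydronephrosis was enrolled. Prospective controls of that period could include such cases too. For nuchal translucency, cystic hygroma and skin edema qualify separately under Appendix A, isolated cases are capped at 5% per group, and no direction of bias can be given.

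**Conclusion.** The point holds in limited form. As written, the plan allows dichorionic twins from before 22 Dec 2021 on the control side alone. The mismatch concerns retrospective controls from that period only; from that date the plurality rule is the same for both groups.

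The size is uncertain. Under the assumed range of 3-10% excess twins at 1.5-2.5 times the charges, the control mean rises 1.5-15%, against a targeted 20% reduction, and type I error is about 5.3-22.5% (8.5% at 6% and twofold). At 1-3% twins and up to twofold charges it is about 5-6%. These figures assume no sequenced twins to offset the excess, no adjustment, and twins costing more than singletons.

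A reader might reach a worse figure, up to 45%, by treating the rise in the mean as a uniform shift of all log charges. That is not correct when only a subset is affected. Nor do the documents establish that the whole log will be used; this is inferred from the missing window. The point is an inexpensive improvement to a non-randomized co-primary comparison, not evidence that the comparison is invalid.

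**What to change.** In section 4.2.3, state that a retrospective control must meet the plurality and anomaly criteria in force for the sequenced group on the date the anomaly was diagnosed. Dichorionic twins then count as controls only from 22 Dec 2021, and the hydronephrosis and nuchal translucency changes are handled by the same rule.

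In section 5.3, include plurality and enrollment period as fixed covariates in the sequenced-versus-unsequenced charge and perinatal comparisons, whether or not a baseline difference is significant. Add a singleton-only sensitivity analysis.

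Do not require that controls satisfy the criteria of every protocol version. Version 1.0 required a negative prenatal or postnatal microarray for controls, so that rule would also remove controls who never had one.

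The cost is a few early twin controls and slightly more analysis work. Screening date and twin status are already collected.

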#### 3.2.3.2 Exclusion Criteria

- 1. Prenatal or postnatal (prior to neonatal discharge) CMA with pathogenic or likely pathogenic variants that are related to the prenatal ultrasound finding
- 2. Maternal or paternal age less than 18 years old
- 3. Proven infectious, teratogenic, or other genetic cause of fetal anomaly
- 4. Positive prenatal NIPT screening for trisomy 21, 18 or 13. Positive 22q11.2 prenatal NIPT testing with consistent ultrasound findings is also an exclusion.
- 5. For twin gestation, anomalies in both fetuses (NT, IUGR, or structural anomaly)
- 6. Monochorionic diamniotic (MCDA) and monochorionic monoamniotic (MCMA) twins as well as higher-order multifetal gestations.
- 7. Termination of the fetus or intrauterine fetal demise (IUFD) within 3 weeks of date of initial anomaly diagnosis
- 8. Language barrier (non-English or Spanish speaking)
- 9. Delivery at a site other than one of the study centers or associated hospitals
- 10. Unable to access prenatal or neonatal records

[figure not shown]

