The study will determine, in a sequential population of pregnancies with selected fetal structural anomalies and a negative or non-causal chromosomal microarray (CMA), the frequency of pathogenic, likely pathogenic, and uncertain genomic variants identifiable by sequencing. To determine the impact of this information on clinical care, a control population of unsequenced pregnancies with similar structural anomalies will be prospectively recruited and the infants from both cohorts will be followed up to 1 year of age. Due to limited prospective enrollment of the controls, a portion of the unsequenced pregnancies will be enrolled retrospectively through medical record review. This study component will evaluate differences in healthcare management and cost through discharge from hospital post-delivery, and perinatal and infant outcomes through 1 year of life. The educational, counseling and psychosocial impact of sequencing results during the prenatal period, in the nursery and through 1 year of life also will be evaluated. The retrospective unsequenced pregnancies will not be included in 1-year follow-up, as they will be enrolled under a waiver of consent. Since the analytical and clinical tools needed for the full translation of sequencing into care are still developing, optimization of bioinformatic tools to improve identification of pathogenic and likely pathogenic mutations associated with prenatal phenotypes of established disease genes will be investigated, as well as identification of new genes associated with presently undiagnosed fetal/neonatal phenotypes. This study will provide an in-depth evaluation of the prenatal diagnostic value of sequencing prior to its responsible introduction into practice and will provide independent data to guide its translation.

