either in person or electronically, parental samples will be collected if needed, and genome sequencing will proceed. This defines the time enrolled in the study. Parents declining participation at this time will be considered as having refused consent; these participants may be offered participation in the unsequenced prenatal group if eligibility criteria are met. Those choosing to terminate their pregnancy based on ultrasound/CMA findings are ineligible.

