#### 4.2.2 Unsequenced prenatal group

The prospective unsequenced prenatal group will include participants that decline invasive testing and those that plan to have invasive testing but decline sequencing (Figure 1). For participants that plan to have invasive testing but decline sequencing, enrollment into the study will occur after the clinical karyotype/CMA results are confirmed negative and the participant signs the prenatal unsequenced consent. Participants that decline invasive testing will be enrolled at the time of diagnosis of the fetal anomaly and they sign the unsequenced prenatal group consent. Women from this group who later elect invasive testing are not eligible to enroll in the prenatal sequencing group but will be included in the unsequenced prenatal analyses if the karyotype and CMA are confirmed negative or non-causal.

Postpartum genetic testing (karyotype and CMA) and genomic sequencing may be performed at the discretion of the clinical care team as part of routine care. Continued follow-up of the pregnancy and 1-year postpartum period will not take place if a pathogenic or likely pathogenic causal CMA is identified prior to neonatal discharge.

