**Table 2. Summary of Data Collection** 

Two weeks after discussion of study results or 4 weeks after enrollment for the unsequenced prenatal group	Maternal and paternal psychosocial survey
Delivery and neonatal care	
 
Pregnancy complications & delivery outcomes
 
Neonatal phenotype and outcomes
 
Coordinator and physician review of medical records to assess change in management (sequencing group only)
 
Results of clinical care ordered genetic testing for unsequenced group including karyotype/CMA and any subsequent sequencing
 
Reports of healthcare utilization and charges from admission for delivery to discharge (maternal)
 
Healthcare utilization and charges from delivery until discharge or death (neonatal)
 

One month post discharge (prospective only)	Maternal and paternal psychosocial survey
12 months postpartum (prospective only)	
 
Maternal and paternal psychosocial survey
 
Infant weight and length, genetic testing post discharge, and healthcare utilization by maternal self-report
 

	Ages and Stages questionnaire (ASQ-3)
--	---------------------------------------

Neonatal phenotypes will be re-evaluated within one week of birth and infant phenotypes at 12 months to identify additional clinical features. If significant new clinical findings are discovered, the sequencing variants will be re-evaluated immediately by the local team and any new diagnoses confirmed and reported by the study staff to the neonatologist, pediatrician, or other appropriate care provider who will report this to the family in concert with the study coordinator. A copy of de-identified genetic reports (CMA and/or sequencing) will be transferred to the DCC for all enrolled patients in the unsequenced group.

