## 5.3 Prenatal Sequencing and Prenatal Unsequenced Groups

Clinical management including health care utilization and cost, and pregnancy and neonatal outcomes will be compared among the prenatal sequencing group and the unsequenced prenatal group (prospective and retrospective). Women whose fetus or neonate is found to have pathogenic or likely pathogenic causal findings on CMA prior to neonatal discharge will be excluded from these analyses. Twelve month postpartum outcomes will be compared only among those individuals enrolled prospectively. Initially, demographic data and severity of ultrasound findings will be compared to ensure there are no significant differences between the two study groups (prenatal sequencing and unsequenced prenatal group). If differences are found, the covariates will be adjusted for in the analyses.

Categorical variables will be reported as the number and frequency and associations assessed by the Pearson's chi-square or Fisher's Exact test. The distributions for continuous variables will be assessed for normality and transformed to fit a normal distribution if possible. Normal distributions will be reported as mean and standard deviation and compared with the t-test, and non-normal data will be reported as median and interquartile range and compared with the Mann-Whitney U test.

For each outcome, if the study groups show a significant difference, interactions will be tested and subgroup analyses conducted if the interaction is significant (p<0.05). Pre-specified subgroup analyses include maternal age, race/ethnicity, fetal sex, and type of anomaly (lethal vs non-lethal).

The amount of missing data, missing data patterns, and identification of variables associated with missingness will be explored to inform the primary and sensitivity statistical analyses. Analytic techniques used to address missing data bias will be used as appropriate. A two-sided nominal p-value less than 0.05 will indicate statistical significance.

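### The genetic-cause exclusion for retrospective controls has no as-of date, so chart review can remove a control for a postnatal diagnosis that would not remove a sequenced case

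*Combined protocol and SAP*

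**What the plan says.** All references are to the current protocol (version 1.8), which added the retrospective control group.

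- **Selection of controls.** Section 1.1 says that "a portion of the unsequenced pregnancies will be enrolled retrospectively through medical record review". The share of the 350 is not given. Section 4.2.3 draws them from the screening log and adds: "Participants will be considered enrolled at the time of diagnosis of the fetal anomaly".
- **Criterion 3.** Section 3.2.3.2 excludes "Proven infectious, teratogenic, or other genetic cause of fetal anomaly". It names no date, no type of test, and does not say whether the cause must be known before birth. The same words stand in sections 3.2.1.2 (sequenced) and 3.2.2.2 (prospective controls).
- **Criterion 1 on the same list** does carry a limit: "Prenatal or postnatal (prior to neonatal discharge) CMA with pathogenic or likely pathogenic variants that are related to the prenatal ultrasound finding".
- **Later testing.** Section 4.2.2, which opens with the prospective group, says that after birth "genomic sequencing may be performed at the discretion of the clinical care team as part of routine care". Table 2 (section 4.6) collects "Results of clinical care ordered genetic testing for unsequenced group including karyotype/CMA and any subsequent sequencing", in a row not restricted to prospective participants.
- **Sequenced cases.** Section 4.2.1 makes a causative karyotype, CMA or other non-sequencing result a screen failure when it is known before sequencing. Once the results are negative, consent is signed and sequencing goes ahead: "This defines the time enrolled in the study".
- **Analysis stage.** Section 5.3 has one genetic exclusion, covering both groups: "Women whose fetus or neonate is found to have pathogenic or likely pathogenic causal findings on CMA prior to neonatal discharge will be excluded".

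**The concern.** The criterion is worded alike in all three groups but is not applied from the same vantage point. For sequenced cases and prospective controls it is judged during pregnancy, when a later diagnosis cannot yet be seen. For retrospective controls it is judged from a chart that may already hold a postnatal sequencing or panel result. An abstractor who reads the words literally would exclude such a control. A sequenced case with the same condition stays, because its variant is the study result (section 4.10.1, item 1).

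Sections 3.1 and 5.3 pool retrospective and prospective controls for hospital charges, the second primary outcome, and for the perinatal outcomes. Removing monogenic disease from the controls alone would make the groups differ for a reason unrelated to sequencing. The amendment history says the retrospective group was added because prospective control recruitment was not feasible, so its share may be large. Sites could also read the criterion differently from one another.

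**Working it through.** **Step 1. Timing, side by side.**

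| Group | When criterion 3 is judged | Monogenic diagnosis made later |
|---|---|---|
| Sequenced | Before study sequencing (3.2.1.2, 4.2.1) | Retained; it is primary outcome 1 |
| Prospective control | In pregnancy, at enrollment (4.2.2) | Retained; only a causal CMA before neonatal discharge removes (5.3) |
| Retrospective control | Not stated; applied at record review | Open: removed on a literal reading of 3.2.3.2, retained on the reading suggested by 4.2.3, 4.6 and 5.3 |

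**Step 2. The plan's own power figure.** Inputs from section 5.1: mean charge 277,902, SD 389,484, 500 sequenced, 300 controls, ratio 0.80, two-sided alpha 0.05, stated power 80%.

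- CV = 389,484 / 277,902 = 1.40; log-scale SD = √ln(1 + CV²) = 1.042.
- SE = 1.042 × √(1/500 + 1/300) = 0.0761; |ln 0.80| / SE = 0.2231 / 0.0761 = 2.93.
- Power = Φ(2.93 − 1.96) = 83.4%. With the Mann-Whitney efficiency factor √(3/π), it is 81.7%.

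The stated 80% is reproduced within 2 points by the Mann-Whitney version, which is section 5.3's fallback test.

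**Step 3. Controls that could be lost.** These inputs are assumptions:

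- Diagnosable share g = 9.4%, the yield in section 5.1 (22/234), carried over to unsequenced controls.
- Share f of those with a proven cause in the chart: 25% to 100%.
- All 300 analysable controls are retrospective.

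Lost = 300 × g × f: 300 × 0.094 × 0.25 = 7, and 300 × 0.094 × 1 = 28. If only a share h of controls is retrospective, f is replaced by h × f. With h = 0.5 and f = 0.5 the loss is again 300 × 0.094 × 0.25 = 7.

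**Step 4. Effect on the comparison.** Let m be the mean cost of diagnosable infants relative to the others. The documents give no value for m, so it is varied from 0.5 to 3. With no true effect, the apparent ratio of mean charges (sequenced to control) is

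[(1 − g) + g·m] ÷ {[(1 − g) + (1 − f)·g·m] / (1 − f·g)}.

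Example with m = 2 and f = 0.25: 1.094 ÷ (1.047 / 0.9765) = 1.020. With m = 2 and f = 1: 1.094 ÷ 1 = 1.094.

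The log-scale shift, which is the one relevant to a test on transformed charges, is g·ln m − (1 − f)·g·ln m / (1 − f·g). Adding it to ln 0.80 in step 2, with the reduced control count and the same log SD, gives the chance of a significant result when the true ratio is 0.80 (83.4% without any removal).

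| m | f | Ratio of means, no true effect | Log-scale (geometric) ratio | Chance of significance at true 0.80 |
|---|---|---|---|---|
| 0.5 | 25% | 0.989 | 0.985 | 87% |
| 0.5 | 100% | 0.953 | 0.937 | 96% |
| 2 | 25% | 1.020 | 1.015 | 77% |
| 2 | 100% | 1.094 | 1.067 | 52% |
| 3 | 25% | 1.038 | 1.024 | 74% |
| 3 | 100% | 1.188 | 1.109 | 33% |

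With g between 6% and 15% and the same ranges of f and m, the ratio of means under no effect runs from 0.93 to 1.30. If all groups used comparable timing, this source would contribute nothing (ratio 1.00).

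**The case against.** The strongest reply is that criterion 3 is simply the entry criterion carried over. It matches the prospective wording exactly, and the amendment history says it was meant for anomalies with a known cause and was given to controls to match the sequenced group. Section 4.2.3 treats retrospective controls as enrolled at anomaly diagnosis. Section 5.3 removes only causal CMA findings. Table 2 collects later sequencing on controls, which fits better with keeping them than with discarding them.

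Much of this stands. A reader might infer that the plan orders removal of any control with a postnatal diagnosis; no section says so. The reply still does not close the gap, because criteria 1, 7 and 9 of the same list depend on events after anomaly diagnosis. The deemed enrollment date therefore cannot be the as-of date for the whole list. Gestational age (3.2.3.1, item 4) and termination or fetal demise (3.2.3.2, item 7) were tied to the anomaly date; criterion 3 was not.

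A reader might also infer that the bias runs against sequencing and could cancel the 20% reduction the trial is sized for. The documents support neither inference. Diagnosed infants may cost more, but early death or redirected care could make them cost less, and then the bias reverses. A shift close to 20% at the planned 9.4% yield needs every control to be retrospective, every diagnosable control to be diagnosed, and threefold costs; even then the log-scale shift is about 11%. Section 4.6 ends retrospective follow-up at delivery discharge, so the 100% end is a bound and not an expectation.

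**Conclusion.** The point holds as an unspecified as-of date that permits selection on later information in one group only, within a comparison that carries a primary outcome. It is more than missing detail, because the criterion applied as written can remove controls whose sequenced counterparts are kept. It is less than a demonstrated bias: removal is one literal reading, and other sections lean the other way.

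Direction and size are unknown. At the 9.4% yield, with 25% to 100% diagnosed and all 300 controls retrospective, 7 to 28 controls are lost. The apparent cost ratio under no effect is then 1.02 to 1.09 if such infants cost twice as much as the others, or 0.99 to 0.95 if they cost half as much. The share diagnosed, the retrospective share, the cost multiples and the transfer of 9.4% to unsequenced controls are all assumptions, and a smaller retrospective share reduces the effect.

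**What to change.** Reword criterion 3 in section 3.2.3.2 so that it counts only causes established by the point comparable to sequenced-group enrollment. That means the prenatal non-sequencing work-up already applied in sections 3.2.1.2 and 4.2.1: karyotype or CMA, gene panel, infection and teratogen exposure. Keep the separate rule on CMA before neonatal discharge. Retain, or restore, retrospective controls whose only genetic diagnosis came from later sequencing or panel testing.

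The date of anomaly diagnosis is a tempting cut-off because section 4.2.3 uses it, but it should not be adopted. Diagnostic testing usually follows the anomaly finding. Controls with a causal karyotype, panel or infection result in the following weeks would stay in, while equivalent sequenced candidates are screened out. That would create the opposite imbalance.

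Sections 3.2.3.2, 4.2.3, 4.6 (Table 2) and 5.3 should be reconciled to the chosen rule. Report the number of retrospective controls excluded under criterion 3, with the date and type of each diagnosis, and add a sensitivity analysis of charges and perinatal outcomes on those exclusions.

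The cost is one clause in the eligibility criteria, one sensitivity analysis, and a re-check of the charts screened out under criterion 3.
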